1. Pregnant women in the EXE group gain less weight than those in the MOT group
2. Pregnant women in the MOT group gain less weight than those in the CON group.

Exploratory outcomes

- Complementary data on levels of physical activity are determined using doubly labeled water, questionnaires, and additional data from the activity tracker.
- Clinical and metabolic health parameters in mother and offspring.

Section 3: Study Methods

Trial design

Single-site three-armed randomized controlled trial.

Brief description of the interventions

The targeted physical activity level for all participants in the EXE and MOT groups is at least 30 minutes per day at moderate intensity as recommended to healthy pregnant women [6].

Standard care control group (CON)

The CON group is offered standard care at the hospital.

Structured supervised exercise training (EXE)

The training is performed in groups and supervised by health professionals. It consists of three weekly one-hour exercise sessions at a moderate intensity, including two land exercise sessions and one water exercise session.

Motivational counseling supported by health technology (MOT)

This intervention comprises four individual and three group counseling sessions during the pregnancy as well as weekly SMS-reminders. The overall focus of both the individual and group counseling sessions is to create a climate that taps into what already motivates the participants to increase or maintain their physical activity level. The activity trackers are used as an intervention element to motivate the participants to increase their physical activity levels. The weekly SMS-reminders have supportive and motivating content and are used to encourage the participants to achieve a moderate physical activity level.

Changes of the intervention during the COVID-19 pandemic

During the COVID-19 pandemic, EXE is converted to exercise at home with online group sessions. MOT is also held online. As much data as possible will be collected during the pandemic, but some clinical data may not be possible to obtain.

Randomization

After a one-week baseline period where the physical activity level is measured by the activity trackers, the women are randomly assigned in a 1:2:2 ratio to CON, EXE or MOT. The randomization is performed via a numbered randomization list administered through the electronic database REDCap and the investigators are blinded to the randomization procedure.

Sample size

[figure not shown]
Primary outcome

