The expected lost-to-follow-up rate needs to be considered and added to the sample size. Therefore, we will include 44 participants in CON and 88 participants in EXE and MOT, respectively, in total 220 women, based on an expected lost-to-follow-up rate of 20%, as seen in similar exercise studies in pregnant women [6,10,12,19]. This should leave 35 participants in CON (0.8×44) and 70 participants in each of the two intervention groups (0.8×88), which will give sufficient power for analysis of the primary outcome.

Secondary outcome

Based on a comparable intervention study with exercise training [21], the estimated GWG in the intervention and control groups had standard deviations of 4 kg. Thus, in the present study, 33 women in the CON and 66 in each of the intervention groups (EXE and MOT) are needed to detect a difference of 2.8 kg between the control and the intervention groups with a power of 0.80 and two-sided α -level of

0.05. The sample size calculation to this secondary outcome was performed during the intervention but before the intervention was completed.

Framework

The hypothesis testing framework is based on model comparisons using the Likelihood Ratio Test of equality between null and alternative models.

Statistical interim analyses

No interim analyses will be performed. The trial will not be stopped early as a result of data analyses.

Timing of final analysis

The final analysis of the primary outcome will be performed when the last participant has passed GA week 28+6. The final analysis of the secondary outcome will be performed when the last participant gives birth.

Timing of outcome assessments

The primary outcome is measured continuously (24/7) from randomization to GA week 28+6. The secondary outcome is measured at baseline (max. GA week 15+0), GA week 28+0-6, GA week 34+0-6 and at delivery.

Section 4: Statistical Principles

Confidence intervals and P values

The level of statistical significance is 5%. The primary analysis containing two hypotheses will be tested at a significance level of 2.5% each to control the family-wise type I error. Wald-based 95% confidence intervals will be given for all reported estimates.

Adherence, protocol deviations, and analysis populations

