Number of participants	N=220
Age (years)	Mean ± (SD) or median (IQR)
Weight (kg)	Mean ± (SD) or median (IQR)
BMI at inclusion (kg/m ²)	Mean ± (SD) or median (IQR)
Gestational age at inclusion (weeks)	Mean ± (SD) or median (IQR)
Education level (1-3)	n/Total (%)

The number of babies (no.)	Mean ± (SD) or median (IQR)
Marital status (married or have partner/not)	n/Total (%)
Alcohol consumption before pregnancy (serving/week)	Mean ± (SD) or median (IQR)
Alcohol consumption during pregnancy (serving/week)	Mean ± (SD) or median (IQR)
Smoking status (current smoker)	n/Total (%)
Employed (yes/no)	n/Total (%)
Physical activity at work (active/sedentary)	n/Total (%)
Fertility treatment (no.)	n/Total (%)
Self-reported weekly physical activity level during pregnancy before inclusion (≤30 minutes or 30-60 minutes)	n/Total (%)
Minor health problems (no.)	n/Total (%)
Pelvic pain during pregnancy (yes/no)	n/Total (%)
Pelvic pain before pregnancy (yes/no)	n/Total (%)
Total cholesterol (mmol/L)	Mean ± (SD) or median (IQR)
HDL (mmol/L)	Mean ± (SD) or median (IQR)
LDL (mmol/L)	Mean ± (SD) or median (IQR)
HbA1c (mmol/mol)	Mean ± (SD) or median (IQR)
Triglycerides (mmol/L)	Mean ± (SD) or median (IQR)
Steps per day (average steps/day)	Mean ± (SD) or median (IQR)
Active calories (calories/day)	Mean ± (SD) or median (IQR)
Moderate to vigorous physical activity (minutes/week)	Mean ± (SD) or median (IQR)
Active time (minutes/day)	Mean ± (SD) or median (IQR)
Floors walked (no./week)	Mean ± (SD) or median (IQR)
Minimum heart rate (beats/min)	Mean ± (SD) or median (IQR)
Average heart rate (beats/min)	Mean ± (SD) or median (IQR)
Maximum heart rate (beats/min)	Mean ± (SD) or median (IQR)
Resting heart rate (beats/min)	Mean ± (SD) or median (IQR)
Metabolic equivalent of task (MET/day)	Mean ± (SD) or median (IQR)
Move IQ (%type of physical activity)	Mean ± (SD) or median (IQR)

Section 6: Analysis

Outcome definitions

Primary outcome

The primary outcome, MVPA, is measured continuously (24/7) by an activity tracker and will be presented in minutes per week from randomization to GA week 28+6.

Secondary outcome

The secondary outcome is GWG, i.e. weight gained from the onset of the pregnancy to giving birth. GWG is determined as the difference between body weight on the day of birth and preconception body weight.

All other outcomes will not be presented with hypothesis testing, and they will be represented as exploratory outcomes.

Analysis methods

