The treatment effects for the primary and secondary outcomes will be presented as mean differences between the treatment groups adjusted for physical activity at baseline. These values will be estimated from a multiple linear regression model. Analysis of the primary outcome based on multiple imputed datasets will be performed as a sensitivity analysis. The imputations will be performed using the R package “mice” [24]. 25 imputed data sets will be generated using the seed 24658. The imputations will be constructed on the following baseline covariates (body weight, age, group allocation, physical activity at baseline, socio-economic status). In addition, a sensitivity analysis will be performed to investigate whether the COVID-19 pandemic had an impact in the three study groups.

Missing data

The primary outcome will be measured by the activity tracker continuously (24/7) during the intervention. Possible missing data from the tracker due to not wearing the device or other reasons (e.g. skin rash) will be handled according to the predefined inclusion of the data in the analysis. For the primary outcome, a week will be included in the analysis if the week has four or more days with complete data. A day that has six hours or more of non-wear time will be excluded and considered a missing day.

Additional analyses

Analyses describing associations between the level of physical activity, as measured by the activity tracker, and the secondary and exploratory outcomes in all three groups will be performed.

Harms

Information about adverse events (AEs) and serious adverse events (SAEs) will be registered and reported. The AEs/SAEs will be reported as frequency and percentage in the trial groups.

Statistical software

The statistical analysis will be performed using the latest version of R [24].

References

- [2] World Health Organisation (WHO). *Good Maternal Nutrition. The best start in life.* 2016.

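### The gestational weight gain model leaves out the two weights that measure gain before randomisation; adding both may narrow the intervals at almost no cost

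*SAP*

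**What the plan says.** Section 6 of the SAP (Analysis methods) sets one adjustment for both outcomes: effects are "mean differences between the treatment groups adjusted for physical activity at baseline", and "These values will be estimated from a multiple linear regression model". No other covariate is named for GWG.

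The outcome and its timing are set elsewhere in the SAP:

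- Section 6, Outcome definitions: "GWG is determined as the difference between body weight on the day of birth and preconception body weight".
- Section 3, Timing of outcome assessments: "The secondary outcome is measured at baseline (max. GA week 15+0), GA week 28+0-6, GA week 34+0-6 and at delivery".
- Section 3, Randomization: "After a one-week baseline period where the physical activity level is measured by the activity trackers, the women are randomly assigned".
- Section 3, Sample size, secondary outcome: with an SD of 4 kg, 33 women in CON and 66 in each intervention group are "needed to detect a difference of 2.8 kg between the control and the intervention groups with a power of 0.80", at a two-sided 5% level.

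Body weight is listed in the baseline table. It is also a predictor in the multiple imputation planned for the primary outcome. It is absent from the one model whose outcome is a weight change.

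**The concern.** GWG is the sum of two pieces:

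GWG = (baseline weight − preconception weight) + (day-of-birth weight − baseline weight).

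The first piece is complete before allocation, at a gestational age of at most 15+0 weeks. No intervention can change it, so in the group contrasts it is noise. Because it predates randomisation, adjusting for it is legitimate. Baseline physical activity gives no direct handle on it, whereas the two weights together determine it exactly.

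What is at stake is the width of the confidence intervals for the two GWG contrasts, EXE versus MOT and MOT versus CON. Validity is not in question.

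**Working it through.** **The plan's own figure.** Equal allocation gives 2 × (1.96 + 0.84)² × 4² / 2.8² = 32.0, rounded up to 33 per arm. This is the stated CON number, and 66 is its double. At the 1:2 allocation actually used, 1.5 × (1.96 + 0.84)² × 4² / 2.8² = 24.0, so 25 and 50 would do. With 33 and 66 the standard error is 4 × √(1/33 + 1/66) = 0.853 kg, and power is Φ(2.8/0.853 − 1.96) = 0.907. The stated aim is therefore met with no covariate at all.

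**Inputs.**

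- From the SAP: total SD of GWG 4 kg; 35, 70 and 70 women after the expected 20% loss.
- Assumed, because the SAP gives neither: early-gain SD s0 of 1 or 2 kg, and its correlation r with later gain between −0.3 and +0.3.

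**Variance removed.** The later-gain SD s1 solves s0² + s1² + 2·r·s0·s1 = 16. Once both weights are in the model, the residual variance of GWG is (1 − r²)·s1², so the share removed is 1 − (1 − r²)·s1²/16.

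**Cost of two covariates.** With 175 women in three groups and q covariates, the expected inflation of a contrast variance is 171/(171 − q). Going from one covariate to three multiplies it by 170/168 = 1.012.

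| s0 (kg) | r | Removed | Net of cost |
|---|---|---|---|
| 2 | −0.3 | 0.037 | 0.025 |
| 2 | 0 | 0.250 | 0.241 |
| 2 | +0.3 | 0.516 | 0.511 |
| 1 | −0.3 | 0.004 | −0.008 |
| 1 | 0 | 0.062 | 0.051 |
| 1 | +0.3 | 0.269 | 0.260 |
| 2 | −0.45 | 0.000 | −0.012 |

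The last row is the worst case: the weights carry no information and only the cost remains.

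**Detectable difference** (80% power, two-sided 5%) = 2.80 × 4 × √(1 − net) × √(1/n1 + 1/n2). At s0 = 2 kg:

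- EXE versus MOT (70 and 70): from 1.89 kg to 1.87, 1.65 and 1.32 kg for r = −0.3, 0 and +0.3.
- MOT versus CON (70 and 35): from 2.32 kg to 2.29, 2.02 and 1.62 kg.

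**Simulation.** Trials of 35/70/70 women, with preconception weight SD assumed at 15 kg and baseline activity kept in every model, agree with the formula. For EXE versus MOT the reductions were 1.9%, 24.2% and 50.5% at s0 = 2 kg, and −0.4%, 4.6% and 26.7% at s0 = 1 kg.

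**Why both weights.** A single weight mostly reflects differences in body size. At s0 = 2 kg and r = 0, with preconception weight unrelated to gain, preconception weight alone gives −0.7%, baseline weight alone −0.1%, and both together 24%. If preconception weight correlates −0.3 with GWG (assumed), the figures are 8%, 5% and 30%. That joint figure lies between 24% and 33%, depending on how the correlation divides between early and later gain.

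**Missing baseline weight.** The SAP gives no rate but warns that during the pandemic "some clinical data may not be possible to obtain". Its imputation provision does not extend to GWG: "Analysis of the primary outcome based on multiple imputed datasets will be performed as a sensitivity analysis". With 10% missing at random (assumed), s0 = 2 kg and r = 0, the 24% gain becomes:

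- 22% if the missing value is predicted from preconception weight;
- 16% if those women are dropped;
- 3% if the plain sample mean is filled in.

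At 20% missing, prediction keeps 19% and the other two keep 6% or less. Where the weights are nearly uninformative (s0 = 1 kg, r = −0.3, 10% missing), dropping women costs about 12% of variance, against 0.8% with prediction.

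**The case against.** The planned analysis is valid, explicit and powered above its stated target, so nothing in the plan fails. The benefit also cannot be fixed from the SAP, because the early-gain SD and its correlation with later gain are both assumed, and the range includes zero. The gain of about half the variance is the most favourable corner of that range. All of this stands, and it limits the point to precision.

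The SAP does not say how preconception weight is obtained. For eligibility it accepts the first weight measured in pregnancy as a substitute. If the same substitution were used for GWG, the two weights would carry little separate information for those women. This also stands as a limit, but it does not remove the benefit: with 30% of women substituted at random (assumed; s0 = 2 kg, r = 0), a gain of about 18% remains and no bias appears.

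Finally, the missing-weight rule answers a problem that exists only because a covariate is added. That is true, and it is the reason for the rule: without it, the added covariate could cost participants.

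The power argument is weaker than it looks. The 2.8 kg refers to control versus intervention, and the SAP gives no target difference for EXE versus MOT, its first GWG hypothesis. If that difference were 1.4 kg (assumed, half of 2.8), power at 70 and 70 would be about 0.54 as planned and about 0.66 after a 24% variance reduction.

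**Conclusion.** The concern holds as a matter of efficiency. The GWG model omits two pre-randomisation weights that the plan already schedules or needs, and that together measure a part of the outcome the intervention cannot affect. There is no bias and no shortfall against the stated power.

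Under the assumptions above, the net effect on the contrast variance runs from a loss of about 1% to a gain of about half. It is 5% to 24% if early and later gain are uncorrelated and early gain has an SD of 1 to 2 kg. It is close to nil if the two are negatively correlated. The change is worth making because the possible loss is so small beside the possible gain.

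**What to change.** In Section 6, Analysis methods, state that the GWG regression includes preconception weight and baseline-visit weight, both together, alongside baseline physical activity. Leave the definition of GWG unchanged.

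Add a rule for a missing baseline-visit weight. The woman stays in the model, and the value is replaced by its prediction from a linear regression on preconception weight, fitted in all women with both weights and using neither outcome nor group. Do not fill in the plain sample mean, which breaks the pairing between the two weights.

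Make the change before GWG is analysed. It costs two sentences and two degrees of freedom, about 1.2% of variance, and needs no new measurement.

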The primary analysis is an intention-to-treat analysis including all participants as randomized. Also, a dose-response model will be fitted for the EXE and MOT groups to describe the relationship between adherence to the intervention (proportion of attendances) and the attained activity level. This relationship will be compared to the average activity level in the CON group.

Section 5: Trial Population

Screening data

Screening data will not be reported.

Eligibility

Inclusion criteria

- Written informed consent obtained before any trial-related procedures are performed
- A pregnant woman aged 18 years or older
- GA of max. 15+0 weeks
- Ultrasonic confirmed intrauterine pregnancy
- BMI of 18.5-45 kg/m² and body weight below 150 kg calculated from pre-pregnancy weight or first measured weight in pregnancy

- Ability to wear a wrist-worn activity tracker 24/7

Exclusion criteria

- Severe chronic disease
- Structured exercise at moderate to vigorous intensity more than 1 hour per week during pregnancy
- Previous preterm delivery (before GA week 37)
- Obstetric or medical complications
- Multiple pregnancies
- Non-Danish speaking
- Alcohol or drug abuse

Recruitment

The flow chart of the trial will follow the CONSORT guidelines and will include the number of individuals who a) showed interest to participate in the study by filling out a pre-screening questionnaire, b) were assessed for eligibility at screening visit, c) were included in the trial, d) were randomized, e) did not receive allocated treatment, f) were lost to follow-up, g) discontinued the intervention, and h) were analyzed in the end.

Withdrawal/lost to follow-up

If a randomized participant withdraws or is discontinued from the intervention, we will offer to perform all or some of the planned visits. The number/frequency of participants lost to follow-up will be provided for each group and for each visit. If possible, the reasons for participants not completing the trial will be given. Summary of baseline levels for variables reported in the baseline table will be provided for completers and non-completers.

Baseline patient characteristics

Categorical variables will be summarized by frequencies and proportions, and symmetrically distributed continuous variables will be summarized by the mean and standard deviation (SD). Asymmetric variables will be presented as medians and interquartile ranges (IQR).

The table presents the baseline characteristics to be reported.

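### The imputation check for missing MVPA uses only baseline covariates and group, omits weekly MVPA recorded after randomisation, and leaves its unit unstated

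*SAP*

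**What the plan says.** - Section 3 (Timing of outcome assessments): "The primary outcome is measured continuously (24/7) from randomization to GA week 28+6".
- Section 6 (Missing data) makes the week the unit that counts or drops out: "a week will be included in the analysis if the week has four or more days with complete data". A day with six or more hours of non-wear is treated as missing.
- Section 6 (Analysis methods) reports group differences adjusted for baseline physical activity: "These values will be estimated from a multiple linear regression model".
- The same section adds: "Analysis of the primary outcome based on multiple imputed datasets will be performed as a sensitivity analysis". The software is mice, and "25 imputed data sets will be generated using the seed 24658". The predictors are then named: "The imputations will be constructed on the following baseline covariates (body weight, age, group allocation, physical activity at baseline, socio-economic status".
- Section 4 (Adherence, protocol deviations, and analysis populations): "The primary analysis is an intention-to-treat analysis including all participants as randomized".

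The only other sensitivity analysis in Section 6 concerns COVID-19. The SAP does not say whether the imputed quantity is a woman's mean or a single week, nor how a woman with few or no valid weeks enters the regression.

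**The concern.** For a woman who leaves or stops wearing the tracker, her own earlier weeks are the most informative data on the weeks that are missing. The tracker collects them, but the imputation list leaves them out. Of the listed predictors, group and baseline activity are already in the primary regression, so the imputation adds only body weight, age and socio-economic status.

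What this costs depends on the unstated unit. Per woman, the check cannot react to loss driven by early MVPA. Per week, it fills a woman's missing weeks as if they were unrelated to her observed ones. At stake is whether agreement or disagreement between this check and the primary result can be interpreted, in a trial that itself expects 20% loss.

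**Working it through.** **The plan's own figures.** Section 3 (Sample size) gives means of 60, 210 and 150 min/week (CON, EXE, MOT), SD 116, evaluable groups of 35, 70 and 70, and 80% power; Section 4 gives 2.5% per hypothesis. For EXE against MOT the standard error is 116 × √(2/70) = 19.61, and 60/19.61 = 3.06. Subtracting the normal quantile 2.24 leaves 0.82, a power of 79.4%. Simulating the double hypothesis with likelihood ratio tests gives 79.5%. For loss, 35/0.8 = 43.75 and 70/0.8 = 87.5, so 44 + 88 + 88 = 220. The design figures reproduce.

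**Assumptions not in the SAP.** The main simulations use 44/88/88 women, 14 weeks, week-to-week correlation (ICC) 0.4 to 0.8, baseline-outcome correlation 0.5, other listed covariates correlated 0.15 with MVPA, and 0 or 10% of weeks lost intermittently. Weekly runs have 600 trials and 10 imputations; the per-woman run has 1,500 trials and 25 imputations.

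**Reading 1: a woman's mean is imputed and the regression omits women without one.**
- With 20% missing at random, 0.8 × 88 = 70.4 women per intervention arm remain. The expected standard error is 116 × √(1 − 0.5²) × √(2/70.4) = 16.9.
- Simulated EXE−MOT is 59.9 (SE 16.9) from the regression and 59.8 (SE 17.0) after imputation. MOT−CON is 89.9 (SE 20.7) and 89.9 (SE 20.8). The correlation of the two estimates is 0.99. There is no bias to correct here, so this shows only that the two nearly coincide.
- If loss depends on a listed covariate outside the regression (correlation 0.3 with MVPA), imputation cuts the bias from +7.3 to +0.7 min/week.
- If loss depends on the woman's own early MVPA, in EXE only (25% vs 15%), the two analyses carry biases of +22.9 and +22.4, a gap of 0.5.

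**Reading 2: available weeks are averaged and only women with no valid week are imputed.** Such women are 0.2% to 1.6% of the sample in these runs. Estimates move by 0.1 to 0.7 min/week on average.

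**Reading 3: single weeks are imputed from the listed covariates alone.** Leave covariates aside, and let b be the between-woman and w the within-woman variance over T weeks. If every woman has a share f of her weeks imputed independently of her own level, the variance of her completed mean is

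(1−f)²·b + (1−f)·w/T + f·(b+w)/T, against b + w/T with no loss.

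With b = 0.6, w = 0.4, T = 14 and f = 0.2 this is 0.384 + 0.023 + 0.014 = 0.421, against 0.629. The square root of the ratio is 0.82. Uneven loss shrinks the spread less, and the between-imputation term adds a little back. Simulated EXE−MOT at ICC 0.6 with 10% intermittent loss plus dropout:

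| Loss and method | Weeks missing | Bias | True SD | Reported SE | Ratio | Coverage |
|---|---|---|---|---|---|---|
| None | 0 | −0.8 | 14.65 | 15.28 | 1.04 | 95.2% |
| Unrelated, available weeks | 19.6% | −0.7 | 15.17 | 15.67 | 1.03 | 94.8% |
| Unrelated, listed covariates only | 19.6% | −0.9 | 15.23 | 13.50 | 0.89 | 91.3% |
| Unrelated, observed weeks added | 19.6% | −0.7 | 15.04 | 15.68 | 1.04 | 94.8% |
| Low-MVPA EXE women leave more, available weeks | 18.8% | −3.0 | 15.12 | 15.72 | 1.04 | 95.8% |
| Same, listed covariates only | 18.8% | +6.8 | 15.20 | 13.34 | 0.88 | 87.7% |
| Same, observed weeks added | 18.8% | −0.3 | 14.88 | 15.58 | 1.05 | 96.0% |

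The Monte Carlo error of a bias is about 14.65/√600 = 0.6. With listed covariates only, the reported SE after losing a fifth of the weeks (13.50) is below the SE with none lost (15.28).

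Over the ICC range and both contrasts, the SE ratio is 0.85 to 0.90 with 19% to 20% of weeks missing completely at random (coverage about 91%), and 0.92 to 0.96 with 11% missing (about 93%). The EXE−MOT bias under MVPA-related EXE loss is +5.6 to +7.5. A separate simulation, with a woman-mean SD of about 116 and other dropout assumptions, gives SE 15.3 against a true 18.0 under unrelated loss (15.3/18.0 = 0.85) and bias of +12 to +15 under EXE-only MVPA-related loss. With observed weeks added, it gives 16.8 against 17.4 (0.97) and bias near 0.

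**The case against.** - **The per-woman check is not empty.** Weight, age and socio-economic status are in the imputation but not in the regression, and the check corrects loss related to them (+7.3 to +0.7 above). This stands. A reader might infer that per-woman imputation can only repeat the primary result; the listed predictors do not support that. The limit applies to loss driven by early MVPA.
- **Nothing says that weeks are imputed.** One regression of group means points to one value per woman. If weeks are imputed, chained equations may let them predict one another, which the SAP does not expressly forbid. Both points are fair. But the SAP names a predictor list without those weeks, and the list may be followed as written. If the team does intend weeks to predict one another, the fix only records it.
- **Averaging available weeks is fairly benign.** Under MVPA-related EXE loss its bias is −1.7 to −4.9 against a target of 60. In one simulation where loss depended on later unseen weeks, it did better (+0.4 and +0.7) than imputation with observed weeks (+2.0 and +3.7). That run had a woman-mean SD of √(95² + 70²/14) = 97, below the SAP's 116, but the point stands: the fix is not better in every case, and it gives no reason to replace the primary regression.
- **MVPA-related loss in EXE alone is an assumption.** No section suggests it, and without it the bias is absent or small. This stands for bias. The understated standard error under week-level imputation does not need it.
- **Descriptive checks are planned.** In Section 5 (Withdrawal/lost to follow-up), "The number/frequency of participants lost to follow-up will be provided for each group and for each visit", with reasons where possible and baseline summaries for completers and non-completers. These would show an imbalance, not its effect on the estimate.

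**Conclusion.** The point holds as a weakness of the sensitivity analysis. The predictor list leaves out the most informative data, and the unit of imputation is open. Per woman, agreement with the primary result says little about loss driven by early MVPA. If only women with no valid week are imputed, the check barely moves. Per week from the listed covariates alone, the standard error is about 10% to 15% too small with a fifth of the weeks missing, and a difference from the primary result can come from the imputation itself.

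The direction of the standard-error result was the same throughout the assumed ICC range. The bias sizes are illustrations: they rest on assumed dropout, 14 weeks in the main simulations, and assumed week-to-week correlation, none of which the SAP gives.

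A reader might infer that the trial's main result or its error rate is at risk. The SAP does not support that. Section 4 assigns the two 2.5% tests to the primary analysis, and Section 6 makes the imputation a sensitivity analysis only. The primary estimate, its type I error and the sample size are unaffected. The change is worth making because it is cheap.

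**What to change.** Keep the planned baseline-adjusted regression as primary. In Section 6 (Analysis methods), state that mice is run at week level, with the observed post-randomisation weekly MVPA as predictors in addition to the listed covariates and group. Then average each woman's completed weeks from randomisation to GA 28+6, fit the planned regression in each of the 25 data sets and pool. Report by group the number of women with no valid week.

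The cost is a few sentences and modest programming, with no new data. The imputation model becomes larger (about 14 weekly variables for 220 women, if follow-up is about 14 weeks). It still assumes missing at random given the observed weeks, and women with no valid week are still imputed from baseline and group only.
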